9.0 TREATMENT/INTERVENTION PLAN

Patients who have signed the consent form and are deemed eligible for this clinical trial will start therapy with carfilzomib, lenalidomide and dexamethasone (CRd) with the following schedule:

- Length of cycle: 28 days. Treatment window for day 1 of start of each cycle is +/- 7 days. Treatment window for intra-cycle carfilzomib doses is +/- 3 days.
- These cycles will consist of:
 - Carfilzomib
 - Cycle 1: 20 mg/m² IV infusion over 10 minutes on days 1 and 2, then 45 or 56 mg/m² IV infusion over 30 minutes on days 8, 9, 15, and 16 depending on the assigned dose level
 - Cycle 2 - up to 12: 45 or 56 mg/m² IV infusion over 30 minutes on days 1, 2, 8, 9, 15, and 16
 - Lenalidomide
 - Cycle 1 - up to 12: 25 mg oral days 1-21 of 28-day cycle
 - Dexamethasone
 - Cycle 1-4: 20 mg oral or IV on days 1, 2, 8, 9, 15, 16, 22, and 23
 - Cycle 5 - up to 12: 10 mg oral or IV on days 1, 2, 8, 9, 15, 16, 22, and 23

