4.2.1 Dose Limiting Toxicity

1. A DLT is defined as any of the below toxicities with attribution to one or more of the study drugs that occur during Cycle 1. Toxicities that occur in subsequent cycles will be handled through dose modifications but will not figure into the definition of MTD. All AEs should be

considered relevant to determining dose-limiting toxicities and to reporting unless the event can clearly be determined to be UNRELATED to the drug.

Non-hematologic

- \geq Grade 2 neuropathy with pain
- \geq Any Grade 3 toxicity (excluding nausea, vomiting, diarrhea, dexamethasone-induced hyperglycemia, electrolyte abnormalities not clinically significant and require no treatment except oral repletion lasting < 72 hours, or Grade 3 lenalidomide induced-maculopapular rash)
- \geq Grade 3 nausea, vomiting, or diarrhea despite maximal antiemetic/antidiarrheal therapy lasting \geq 7 days
- Grade 3 Creatinine increased \geq 3x baseline or \geq 4.0 mg/dL lasting \geq 7 days
- \geq Grade 3 fatigue lasting for \geq 7 days
- Any non-hematologic toxicity requiring a dose reduction within Cycle 1 except for lenalidomide-induced maculopapular rash and dexamethasone-induced hyperglycemia
- Major bleeding toxicity defined as : \geq Grade 3 hematoma, \geq Grade 3 hemorrhage (specified organ- GI, renal, hematuria/bladder, lung, etc.) \geq Grade 2 Intracranial hemorrhage.

Hematologic

- Grade 4 neutropenia ($ANC < 0.5 \times 10^9/L$) lasting for \geq 7 days
- Febrile neutropenia ($ANC < 1.0 \times 10^9/L$ with a fever $\geq 100.5^{\circ}F$)
- Grade 4 thrombocytopenia (platelets $< 25.0 \times 10^9/L$) lasting \geq 7 days despite dose delay
- Grade 3-4 thrombocytopenia associated with major bleeding
- Any hematologic toxicity requiring a dose reduction within Cycle 1

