9.5 Monitoring

- 9.5.1 Routine labs (CBC, chemistry panel 14, LDH, magnesium, uric acid, phosphate) will be performed on Day 1, 2, 8, 15, and 22 of cycle 1, Day 1 of each cycle thereafter, end of therapy, and 1-year and 3-year after end of therapy. Myeloma tests include serum protein electrophoresis, serum immunofixation, beta-2 microglobulin, quantitative immunoglobulins and serum free light chains assay will be performed at baseline, Day 1 of each cycle, end of therapy, and 1-year and 3-year after end of therapy. Serum Lymphocyte subsets will be performed at baseline, Day 1 of cycle 4, and end of treatment. Routine labs, myeloma labs, and lymphocyte subsets can be performed 24 hrs in advance.
- 9.5.2 For patients with initial baseline 24-hr UPEP samples demonstrating ≥ 100 mg/24 hrs, patients will continue to have 24-hr UPEP samples day 1 of each cycle. Once 24-hr UPEP is < 100 mg/24 hrs, patient can have random UPEP with IFE until achieving negativity. If initial baseline 24-hr UPEP sample is IFE positive and/or < 100 mg/24, patients can have random UPEP samples with IFE until achieving negativity. Once random UPEP and IFE is negative, no further urine samples are needed (unless patient's disease is primarily measurable by 24 hr urines i.e. oligosecretory/hyposecretory)
- 9.5.3 Patients will have clinic visits with H&P or standard progress notes assessing for toxicity/side effects on Day 1 of each cycle, end of therapy, 1-month after end of therapy, 1-year after end of therapy and 3-year after end of therapy. Treatment window for day 1 of start of each cycle is ± 7 days. Treatment window for intra-cycle carfilzomib doses is ± 3 days.
- 9.5.4 At CR/sCR or end of therapy, routine labs (CBC, chemistry panel 14, LDH, magnesium, uric acid, phosphate), myeloma specific tests - serum protein electrophoresis, serum immunofixation, beta-2 microglobulin, quantitative immunoglobulins and serum free light chains assay, lymphocyte subsets, 24-hr urine sample for protein electrophoresis (UPEP) and immunofixation to assess for monoclonal protein in the urine (Bence-Jones proteinuria). A bone marrow aspirate will also be performed to assess the status of minimal residual disease by flow cytometry (Sample sent will be the first bone marrow "pull"). Patient will have clinic visit (relevant clinical laboratories and H&P) 1 month after completing combination therapy to undergo assessment of toxicities/adverse events.

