- h. Bone marrow aspirate and biopsy can be performed +/- 21 days of intended cycle day or achievement of CR/sCR. The first pull bone marrow aspirate will be sent for MRD testing for Multiparametric flow cytometry. Bone marrow aspirate and biopsy will be sent to evaluate for histopathology, flow cytometry (bone marrow immunophenotyping of plasma cells), heavy/light chain immunoglobulin rearrangement. Aspirate lysate will also be sent for cell sorting into CD 138- and + fractions and whole bone marrow lysate for HOTB storage so molecular profiling with GEP and DNA-based sequencing at baseline can be performed as correlative work. For patients, reaching CR/sCR MRD negative timepoint earlier where MRD negative status is confirmed at earlier bone marrow evaluation, bone marrow aspiration and biopsy at end of study will be optional. Otherwise, all other bone marrow biopsies are mandatory.
- i. After study therapy ends, follow-up will be 1 month after study end date. Patients may be followed at more frequent time intervals, and thereafter if clinically indicated. Patients who have progressive disease while on therapy will be followed with restaging scans and laboratory tests as clinically indicated. At disease progression, marrow and FDG-PET/CT are optional but recommended.
- j. For patients with initial baseline 24-hr UPEP samples demonstrating ≥ 100 mg/24 hrs, patients will continue to have 24-hr UPEP samples day 1 of each cycle. Once 24-hr UPEP is < 100 mg/24 hrs, patient can have random UPEP with IFE until achieving negativity. If initial baseline 24-hr UPEP sample is IFE positive and/or < 100 mg/24, patients can have random UPEP samples with IFE until achieving negativity. Once random UPEP and IFE is negative, no further urine samples are needed (unless patient's disease is primarily measurable by 24 hr urines)

- k. FDG-PET scan will be performed on patients at baseline, end of therapy or upon suspicion of progressive disease as clinically indicated. End of therapy FDG-PET scan can be performed +/- 21 days.
- l. Treatment window for day 1 of start of each cycle is +/- 7 days. Treatment window for intra-cycle carfilzomib doses is + 2 days. .

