14.0 BIOSTATISTICS

Phase I:

The goal of the phase I trial is to find the maximum tolerated dose (MTD) of carfilzomib when used in combination with lenalidomide and dexamethason. The trial design is a standard 3 by 3 dose escalation design. The three carfilzomib dose levels that will be explored are listed in Section 4.2.2 and the DLT evaluation window is the first cycle of therapy. The DLT definition is provided in Section 4.2.1.

1. A cohort of three patients will be enrolled at the first dose level (45/mg/m²). If no DLTs are observed in the cohort, the next dose level will be explored.
2. If one DLT is observed in the initial cohort of three, an additional three patients will be treated at the same dose level. If no additional patients have a DLT, the next dose level will be explored.
3. If at any point two or more patients have a DLT at a given dose level, the MTD will have been exceeded and the previous dose level will need to be investigated.
4. If three patients are treated at a potential MTD, the dose cohort will be expanded to six for confirmation.

Using this dose escalation scheme, escalation to the next treatment level is probable if the risk of DLT is low, and the likelihood of escalations decreases as the risk of DLT increases, as demonstrated in table below:

Table Dose Escalation/Toxicity Risk

| | | | | | | |
|---------------------------|-----|-----|-----|-----|-----|-----|
| True risk of Toxicity | .10 | .20 | .30 | .40 | .50 | .60 |
| Probability of Escalation | .91 | .71 | .49 | .31 | .17 | .08 |

The minimum and maximum sample size for the phase I trial is 4 and 18, respectively. It is anticipated that 1-2 patients per month may enroll on this trial; thus, approximately one year or less is anticipated as the accrual period for the phase I study.

Phase II:

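### The ±7-day window on Cycle 2 Day 1 lets the Cycle 1 DLT window fall to 21–23 days instead of 28, because the plan sets no minimum number of observation days.

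*Combined protocol and SAP*

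**What the plan says.** Section 9.0 sets the schedule, "Length of cycle: 28 days", and gives the tolerance in the same bullet: "Treatment window for day 1 of start of each cycle is +/- 7 days". Section 9.5.3 and footnote l of the section 10.0 calendar repeat the tolerance. None of the three exempts Cycle 2 or phase I.

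The DLT period is defined by cycle, not by days. Section 4.2.1 counts toxicities "that occur during Cycle 1", section 9.2.2 equates the first cycle with the DLT window, and section 14.0 says "the DLT evaluation window is the first cycle of therapy". Section 4.2.1 adds: "Toxicities that occur in subsequent cycles will be handled through dose modifications but will not figure into the definition of MTD".

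The last week of the nominal cycle is not empty. Lenalidomide is "25 mg oral days 1-21 of 28-day cycle", which leaves Days 22–28 free of it, and dexamethasone in Cycles 1–4 is also due on Days 22 and 23. Carfilzomib is at 20 mg/m² on Days 1–2 of Cycle 1 and first reaches the assigned level on Day 8.

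**The concern.** Tying the DLT window to a cycle whose end can move by a week either way makes its length depend on scheduling. Two patients with the same toxicity, first seen on Day 25, can be classified differently: a DLT if Cycle 2 starts on Day 29, a later-cycle event outside the MTD if it started on Day 22 or 24.

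Escalation rests on three to six patients per level, so one reclassified event can decide it. It turns 1 of 3 into 0 of 3, which escalates without expansion, or 2 of 6 into 1 of 6. The dose so chosen goes into phase II, and the phase I patients treated at the MTD count in the first Simon stage.

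The early edge of the window also collides with the written schedule. The plan does not say what becomes of the Day 22–28 elements when a cycle starts early.

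**Working it through.** **Inputs.** Cycle length 28 days, so Cycle 2 Day 1 is nominally Day 29 (9.0). Window w from −7 to +7 days (9.0, 9.5.3, footnote l). Lenalidomide Days 1–21; dexamethasone Days 1, 2, 8, 9, 15, 16, 22, 23; carfilzomib at the assigned level on Days 8, 9, 15, 16 of Cycle 1 (9.0). Escalation probabilities from the table in 14.0.

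**Day arithmetic.** Cycle 2 Day 1 = 29 + w. Cycle 1 length = 28 + w. Observation from the first target-level dose (Day 8) = 21 + w. Lenalidomide-free days = 7 + w. Dose-free days after carfilzomib Day 16 = 12 + w.

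| w | Cycle 2 Day 1 | Cycle 1 length | Days observed from Day 8 | Lenalidomide-free days | Carfilzomib-free days | Cycle 1 dexamethasone days falling on Cycle 2 dosing days |
|---|---|---|---|---|---|---|
| −7 | Day 22 | 21 | 14 | 0 | 5 | 22 and 23 |
| −5 | Day 24 | 23 | 16 | 2 | 7 | none |
| 0 | Day 29 | 28 | 21 | 7 | 12 | none |
| +7 | Day 36 | 35 | 28 | 14 | 19 | none |

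The −5 row matters because 4.2.2 requires all first-cycle doses, unless the patient has a DLT, before a patient can support escalation. If the Day 22–23 dexamethasone must be given as separate Cycle 1 doses, Day 24 is the earliest start for an escalation-evaluable patient without a DLT.

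**The plan's own figure.** Under the 3+3 rule, P(escalate) = (1−p)³ + 3p(1−p)²·(1−p)³. At p = 0.30 this is 0.343 + 0.9 × 0.168 = 0.494. At p = 0.10, 0.20, 0.30, 0.40, 0.50 and 0.60 it gives 0.906, 0.709, 0.494, 0.309, 0.172 and 0.082. All six match the table in 14.0 (.91, .71, .49, .31, .17, .08).

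**Effect of a short window.** The documents give no onset times, so onset is an assumption, and every patient is placed at the early edge. Let L be the Cycle 1 length (21 for a Day 22 start, 23 for Day 24). The observed risk p* is:
- constant hazard over 28 days: p* = 1 − (1−p)^(L/28)
- uniform onset over Days 1–28: p* = p × L/28
- uniform onset over Days 8–28: p* = p × (L−7)/21

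Putting p* into the 3+3 formula:

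| Onset assumption | Cycle 2 start | p* at 0.30 | P(escalate) | p* at 0.40 | P(escalate) |
|---|---|---|---|---|---|
| None after Day 21 | Day 22 | 0.300 | 0.49 | 0.400 | 0.31 |
| Constant hazard | Day 24 | 0.254 | 0.59 | 0.343 | 0.41 |
| Uniform Days 1–28 | Day 24 | 0.246 | 0.61 | 0.329 | 0.44 |
| Constant hazard | Day 22 | 0.235 | 0.63 | 0.318 | 0.46 |
| Uniform Days 1–28 | Day 22 | 0.225 | 0.65 | 0.300 | 0.49 |
| Uniform Days 8–28 | Day 24 | 0.229 | 0.65 | 0.305 | 0.48 |
| Uniform Days 8–28 | Day 22 | 0.200 | 0.71 | 0.267 | 0.56 |

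Relative to an on-time start, an early start can only lose events. A late start lengthens the window and can add them.

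**The case against.** The plan has three safeguards, and each does some work. The all-doses rule in 4.2.2 plausibly rules out Day 22 for a patient who is to support escalation. Section 9.3.2 bars a new cycle until the neutrophil, platelet and transaminase criteria are met. Section 9.4.1 requires the appropriate drug to be held for Grade 3 or higher toxicity before the next cycle begins, although the investigator chooses which drug. Together they mean that many toxicities already present on Day 22 would delay Cycle 2, and Cycle 1 would simply run on. What remains exposed is narrower: first onset after an early start and before Day 29, in a patient who was fit to start. None of the three sets a minimum observation time, so that gap stays open.

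A reader might go further in four ways that the documents do not support.
- That a DLT requiring seven days' duration cannot be completed if it begins after Day 15. The holds above would often keep Cycle 1 open, and 4.2.1 requires the toxicity to occur in Cycle 1 without saying that all seven days must elapse there.
- That repeated early starts give 28/21 = 1.33 times the planned dose intensity. This needs the window to compound from each actual start, which the text does not say. It also fails for dexamethasone if Days 22–23 merge with the next Days 1–2, because 6 doses in 21 days is the same rate as 8 in 28.
- That 0.71 and 0.56 are the expected effect. They put every patient at Day 22 and no onset before Day 8, although all three drugs start on Day 1 and a DLT may be attributed to any of them.
- That the tolerance flatly contradicts the 28-day cycle. Section 9.0 states both together, so this is an unresolved edge of a nominal schedule.

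**Conclusion.** The point holds as a gap in the definition of the DLT window. As written, that window can be 21 to 23 days rather than 28, and observation from the first target-level dose can be 14 to 16 days rather than 21. New-onset events between an early Cycle 2 start and Day 29 do not count towards the MTD.

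The effect on escalation is a range. With every patient at the early edge, P(escalate) runs from 0.49 (no late onset) through about 0.59–0.65 to 0.71 at a true risk of 0.30. At a true risk of 0.40 it runs from 0.31 through about 0.41–0.49 to 0.56. If only some patients start early, the effect is smaller. The day counts follow from the text; the probabilities rest on assumed onset and assumed early starts.

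The schedule collision is a separate matter of consistency. At Day 22 the lenalidomide-free days fall from 7 to 0, and two dexamethasone days coincide with Cycle 2 Days 1–2. The passages need reconciling, and which clinical rule applies is for the sponsor.

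**What to change.** In 4.2.1 and 14.0, state that DLTs are counted from Cycle 1 Day 1 through at least 28 calendar days, the protocol's own nominal cycle length, or until Cycle 2 Day 1, whichever is later. Word the 4.2.1 sentence on later-cycle toxicity and the parenthesis in 9.2.2 to match. It should be a minimum: a flat 28-day window would drop Day 29–35 events that now count when Cycle 2 starts late.

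Separately, reconcile the Day 1 window in 9.0, 9.5.3 and footnote l with the 28-day cycle, the lenalidomide Days 1–21 schedule and the Day 22–23 dexamethasone doses. Say also whether the all-doses rule in 4.2.2 covers those two dexamethasone days.

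The cost is a few sentences, with no added patients or procedures. For a patient who starts Cycle 2 early, DLT follow-up runs to Day 28, up to 7 days longer than now. The downside is that some toxicity from Cycle 2 doses given before Day 29 would then count towards the DLT decision, which errs on the conservative side.

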9.1 Cycle 1 adjustments

In Cycle 1, the following adjustments to the dosing schema will be implemented:

- Per FDA label recommendations and standard dosing in previous trials, carfilzomib will be given at a lower dose of 20 mg/m² on Days 1 and 2 of Cycle 1. Initiating carfilzomib at higher doses than 20 mg/m² may increase risk of cytokine release-like syndrome.
- Hydration will be administered prior and subsequent to carfilzomib dosing at the clinical discretion of the investigator or per MSKCC institution standard care practice.

9.2 Dose Modifications

9.2.1 Dose Reductions for Lenalidomide

| Lenalidomide | |
|----------------------------|-------|
| Baseline dose | 25 mg |
| One level dose reduction | 20 mg |
| Two level dose reduction | 15 mg |
| Three level dose reduction | 10 mg |
| Four level dose reduction | 5 mg |

9.2.2 Dose Reductions for Carfilzomib

| | Carfilzomib DL -1 | Carfilzomib DL 1 | Carfilzomib DL 2 |
|--------------------------|----------------------|----------------------|----------------------|
| Baseline dose | 36 mg/m ² | 45 mg/m ² | 56 mg/m ² |
| One level dose reduction | 27 mg/m ² | 36 mg/m ² | 45 mg/m ² |
| Two level dose reduction | 20 mg/m ² | 27 mg/m ² | 36 mg/m ² |

If more than 2 dose reductions are required with Carfilzomib, study treatment will be discontinued and the patient will go off therapy. De-escalation of carfilzomib occurring in patients during first cycle (DLT window) of phase I will count as a DLT.

9.2.3 Dose Reductions for Dexamethasone

| | Dexamethasone Cycles 1-4 | Dexamethasone Cycles 5-10 |
|----------------------------|-----------------------------|------------------------------|
| Baseline dose | 20 mg | 10 mg |
| One level dose reduction | 10 mg | 4 mg |
| Two level dose reduction | 4 mg | 0 mg |
| Three level dose reduction | 0 mg | |

9.3. Hematologic Toxicity

9.3.1 On day 1 of each new cycle, patients must meet the following criteria:

- ANC $\geq 1.0 \times 10^9 /L$
- AST and ALT $< 5 \times ULN$
- Platelet count $\geq 50 \times 10^9 /L$

9.3.2 If these conditions are not met on Day 1 of a new cycle:

- The next cycle of treatment will not be initiated until the above conditions (section 9.3.1) are met. If ANC and platelet counts do not satisfy the requirements above after 2 weeks of withholding treatment, the subject will go off therapy. Transfusions and growth factors are permissible after cycle 1.
- For patients not meeting day 1 criteria (section 9.3.1) for two cycles (non-consecutive), the study drug dose(s) will be modified for the next cycle based on dose reduction tables of section 9.2.

9.3.3 If a patient develops thrombocytopenia or neutropenia during the cycle, then the following actions would take place (see Thrombocytopenia/Neutropenia table below).

| Thrombocytopenia | Lenalidomide | Carfilzomib |
|---|--|-----------------------------------|
| Fall to $< 25 \times 10^9/L$ | Hold both Lenalidomide and Carfilzomib, follow CBC at least weekly or more frequently if clinically indicated. Hold prophylactic anti-coagulation. | |
| Return to $\geq 25 \times 10^9/L$ | Resume lenalidomide at next dose reduction | Resume carfilzomib at full dose.* |
| Subsequent fall to $< 25 \times 10^9/L$ | Hold both Lenalidomide and Carfilzomib, follow CBC at least weekly or more frequently if clinically indicated. Hold prophylactic anti-coagulation. | |
| Return to $\geq 25 \times 10^9/L$ | Resume lenalidomide at next dose level reduction | Resume carfilzomib at full dose.* |

*Carfilzomib may be dose reduced at the clinical discretion of investigator.

| Neutropenia (Absolute Neutrophil Count) | Lenalidomide | Carfilzomib |
|---|---|-----------------------------------|
| Falls to $< 0.5 \times 10^9/L$ or to $< 1.0 \times 10^9/L$ with fever | Hold Lenalidomide and Carfilzomib. Add filgrastim if Grade 3 with fever (single temperature of $38.3^{\circ}C$ or sustained temperature of $38^{\circ}C$ for > 1 hour) or Grade 4. Follow CBC at least weekly or more frequently if clinically indicated. | |
| Returns to $\geq 1.0 \times 10^9/L$ | Resume Lenalidomide at next dose reduction. | Resume Carfilzomib at full dose.* |
| Subsequent drop to $< 0.5 \times 10^9/L$ or to $< 1.0 \times 10^9/L$ with fever | Hold Lenalidomide and Carfilzomib. Add filgrastim if Grade 3 with fever or Grade 4. Follow CBC at least weekly or more frequently if clinically indicated. | |
| Returns to $\geq 1.0 \times 10^9/L$ | Resume Lenalidomide at next dose reduction. | Resume Carfilzomib at full dose.* |

*Carfilzomib may be dose reduced at the clinical discretion of investigator.

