4.2.2 Dose Escalation

The trial will initially enroll 3 patients at the 45 mg/m^2 dose of carfilzomib and escalate to 56 mg/m^2 (Level 2) per table 4.2.2.2. Subjects need to receive all doses in first cycle to be eligible for next cohort dose escalation unless patient has a DLT. If excessive toxicity is observed at the starting dose (Level 1), the study include a further de-escalation dose of 36 mg/m^2 (Level -1)..

Table 4.2.2.1 Dose escalation table

| Dose Escalation Schedule | |
|---------------------------------|---------------|
| Dose Level | Carfilzomib * |
| | |

| | |
|----------|----|
| Level -1 | 36 |
| Level 1 | 45 |
| Level 2 | 56 |

* Doses are stated as mg/m²/dose; max BSA of 2.2 m²

-
-
-
-

Table 4.2.2.2 Dose escalation will follow the rules outlined in the Table below.

| Number of Patients with DLT at a Given Dose Level | Escalation Decision Rule |
|---|--|
| 0 out of 3 | Enter up to 3 patients at the next dose level |
| ≥ 2 | Dose escalation will be stopped. This dose level will be declared the maximally administered dose (highest dose administered). Up to three (3) additional patients will be entered at the next lowest dose level if only 3 patients were treated previously at that dose. |
| 1 out of 3 | Enter up to 3 more patients at this dose level. 
• If 0 of these 3 patients experience DLT, proceed to the next dose level.• If 1 or more of this group suffer DLT, then dose escalation is stopped, and this dose is declared the maximally administered dose. Up to three (3) additional patients will be entered at the next lowest dose level if only 3 patients were treated previously at that dose. |
| ≤ 1 out of 6 at highest dose level below the maximally administered dose | This is the MTD and is generally the recommended phase 2 dose. At least 6 patients must be entered at the recommended phase 2 dose. |

[figure not shown]

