13.0 CRITERIA FOR REMOVAL FROM STUDY

Off-therapy Criteria

Patients with medically concerning grade 3 or 4 adverse events related to drug therapy may be taken off therapy at the discretion of the principal investigator.

- Patients who require more than 2 dose reductions of carfilzomib
- Hematologic toxicity has not completely resolved or resolved to < grade 1 or baseline after 2 weeks of withholding treatment
- Therapy has been held for more than 3 weeks due to treating a grade 3 infection
- Grade 4 non-blistering rash or blistering rash of any grade
- Grade 4 neuropathy
- Grade 4 hypersensitivity reaction
- Patient experiencing significant cardiac event as outlined in section 9.5

- Patient completes the protocol treatment
- Progression of disease
- Patient chooses to go off therapy
- The principal investigator may remove patient from protocol therapy if deemed necessary due to medical conditions, compliance, etc.
- Patient becomes pregnant.

Off-Study Criteria

- Patient requests to be withdrawn from study
- Death
- Physician's determination that withdrawal is in the patient's best interest.

Patient has completed 1- and 3-year evaluation from end of therapy

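### A Cycle 1 cytopenia that ends therapy under 9.3.2 can score as no DLT, and 9.3.2 and 13.0 disagree at the 2-week check

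*Combined protocol and SAP*

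**What the plan says.** **DLT definition.** Section 4.2.1 lists five hematologic criteria: ANC <0.5 for at least 7 days; ANC <1.0 with fever; platelets <25 for at least 7 days despite delay; Grade 3-4 thrombocytopenia with major bleeding; and "Any hematologic toxicity requiring a dose reduction within Cycle 1". The criterion covering any Grade 3 toxicity stands under the non-hematologic heading. Section 9.2.2 adds: "De-escalation of carfilzomib occurring in patients during first cycle (DLT window) of phase I will count as a DLT". Section 14.0 states that "the DLT evaluation window is the first cycle of therapy", and 4.2.1 says that toxicities in later cycles do not enter the MTD.

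**Evaluability.** Section 4.2.2: "Subjects need to receive all doses in first cycle to be eligible for next cohort dose escalation unless patient has a DLT".

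**Starting the next cycle.** Section 9.3.1 requires ANC of at least 1.0 and platelets of at least 50 on Day 1 (all counts × 10⁹/L). If these are not met, 9.3.2 withholds the cycle until they are, and then: "If ANC and platelet counts do not satisfy the requirements above after 2 weeks of withholding treatment, the subject will go off therapy".

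**Holds within a cycle.** Section 9.3.3 acts only at platelets <25, ANC <0.5, or ANC <1.0 with fever.

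**Off-therapy criteria.** Section 13.0 lists: "Hematologic toxicity has not completely resolved or resolved to < grade 1 or baseline after 2 weeks of withholding treatment".

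**The concern.** The MTD rests on the DLT count. Under these rules, lowering the dose by one level for a cytopenia within Cycle 1 counts as a DLT. A Cycle 1 cytopenia slow enough to recover that it ends treatment need not count. The worse outcome for the patient can leave the escalation decision unchanged. No text makes a cohort wait to see whether its patients manage to start Cycle 2.

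The second issue is practical. Sections 9.3.2 and 13.0 both act after two weeks of withheld treatment but name different recovery levels. At that check, staff can face a patient whom one section lets continue and the other takes off therapy.

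**Working it through.** **1. Which counts fall between the rules**

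| Finding in Cycle 1 | DLT under 4.2.1? | Hold under 9.3.3? | Blocks Cycle 2 (9.3.1)? |
|---|---|---|---|
| ANC 0.5 to <1.0, no fever | No | No | Yes |
| Platelets 25 to <50, no major bleeding | No | No | Yes |

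A patient in either row needs no hold or reduction in Cycle 1, so all doses can be given and 4.2.2 treats the patient as evaluable. The two-week limit falls on Day 29 + 14 = Day 43, after the 28-day window. Removal at that point changes nothing in the 3+3 count.

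The event is narrow. By Day 43 the last Cycle 1 carfilzomib dose (Day 16) is 43 − 16 = 27 days past and the last lenalidomide dose (Day 21) is 43 − 21 = 22 days past. Section 9.3.2 also allows transfusions and growth factors after Cycle 1.

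**2. Effect on escalation (illustration)**

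P(escalate) = (1−p)³ + 3p(1−p)⁵, where p is the risk of a counted DLT. This reproduces the table in 14.0:

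| p | .10 | .20 | .30 | .40 | .50 | .60 |
|---|---|---|---|---|---|---|
| Computed | 0.906 | 0.709 | 0.494 | 0.309 | 0.172 | 0.082 |
| Section 14.0 | .91 | .71 | .49 | .31 | .17 | .08 |

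Let the listed-DLT risk be 0.10 and the removal risk r, independent of it. If removals counted, p = 1 − 0.9(1−r).

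| r (assumed) | p | P(escalate) | P(at most 1 DLT in 6) |
|---|---|---|---|
| 0 | 0.100 | 0.906 | 0.886 |
| 0.01 | 0.109 | 0.891 | 0.868 |
| 0.02 | 0.118 | 0.875 | 0.849 |

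For r = 0.01: 0.891³ + 3 × 0.109 × 0.891⁵ = 0.707 + 0.184 = 0.891. The falls in escalation probability are 1.5 and 3.1 percentage points.

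**3. How often a cohort would have to wait**

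Section 14.0 expects 1-2 patients per month. In days from the first entry, each patient ends Cycle 1 at entry + 28 and reaches the two-week limit at entry + 42.

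- Entries at 0, 15, 30: the third patient ends Cycle 1 at 58; the first two limits are 42 and 57.
- Entries at 0, 30, 60: the third ends at 88; the first two limits are 42 and 72.

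At either pace only the last patient's result is outstanding, unless patients enter close together.

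**4. Sections 9.3.2 and 13.0 side by side**

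Take a patient who entered with platelets of at least 75 (the 6.1 minimum) and whose Day 1 count blocks the next cycle.

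- Platelets reach 60 before two weeks: 9.3.2 allows the cycle to start, withholding ends, and the two-week condition in 13.0 is never met. No conflict.
- Platelets still <50 at two weeks: 9.3.2 removes the patient, and so does 13.0. No conflict.
- Platelets first reach 60 at the two-week check: 9.3.2 allows a restart. The count is below baseline and not fully resolved, so the 13.0 criterion is met. Conflict.

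The third case assumes that 60 is still a graded toxicity. The protocol adopts CTCAE 4.0 without reproducing its platelet cut-offs.

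**The case against.** The strongest reply is that 4.2.1 makes a deliberate choice. It reserves hematologic DLTs for prolonged Grade 4 counts, febrile neutropenia, bleeding, or a dose reduction in Cycle 1, and leaves out uncomplicated Grade 3 cytopenia. Removal under 9.3.2 is decided after the stated window. Removals would still appear in the toxicity tables and reach the monitoring committee, and Table 4.2.2.2 says only that the MTD is generally the recommended phase 2 dose. This much stands: the gap lies in the formal escalation rule, not in visibility. It does not explain why a Cycle 1 reduction counts and a treatment-ending cytopenia with Cycle 1 onset does not. The sentence making adverse events relevant "unless the event can clearly be determined to be UNRELATED to the drug" concerns attribution and adds no criterion.

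Three stronger readings are tempting and are not supported.

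- *A brief Grade 4 count also escapes.* Blood counts "will be performed on Day 1, 2, 8, 15, and 22 of cycle 1", so a Grade 4 first found on Day 22 and lasting under 7 days would lead to a lenalidomide reduction only in Cycle 2. But the DLT line can be read with the toxicity, rather than the reduction, falling within Cycle 1. On that reading the event is already a DLT.
- *Sections 9.3.2 and 13.0 conflict for every partial recovery.* They do not, because restarting at the 9.3.1 counts ends the withholding. The sentence opening the 13.0 list, which gives the principal investigator discretion over grade 3 or 4 events, may soften the criterion further; whether it governs every item is unclear.
- *The prior phase 1/2 CRd study gives a removal rate.* Section 3.1 reports Grade 3/4 thrombocytopenia and neutropenia at 17% each. Assuming no overlap and an even spread over 12 cycles, that is 1 − 0.66^(1/12) = 3.4% per cycle. This is the incidence of any such cytopenia. On that even-spread assumption, removal can only be a fraction of it. The higher carfilzomib doses here or early clustering could raise it, but the documents quantify neither.

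**Conclusion.** Both parts hold, and both are minor.

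The DLT gap follows from the text for afebrile ANC of 0.5 to <1.0 and platelets of 25 to <50 without major bleeding. It needs no assumed rate to exist. Its size does: the documents give no removal rate, the event is probably uncommon, and the 1% and 2% figures are illustrations that also assume a 10% listed-DLT risk and independence. They do not show that the MTD would be wrong.

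The conflict between 9.3.2 and 13.0 is confined to the two-week check, for a patient who first reaches the 9.3.1 counts then and is still below baseline. Patients who pass earlier are not affected.

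**What to change.** - **4.2.1, new hematologic criterion:** 'Cytopenia with onset in Cycle 1, not clearly unrelated to study drug, that prevents the start of Cycle 2 after 2 weeks of withholding under 9.3.2; for patients enrolled under the 6.1 cytopenia waiver, only if the failing count is below the patient's own baseline.'
- **4.2.1 and 14.0, window sentences:** allow for this criterion, since its outcome is known only up to 14 days after Cycle 1.
- **4.2.2, cohort closing:** a cohort does not close for escalation until each patient has started Cycle 2, had a DLT, or reached the two-week limit.
- **13.0, hematologic criterion:** use the 9.3.1 counts for starting a cycle and the 9.3.3 return counts for a hold within a cycle.

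The cost is these text edits, a baseline-dependent rule for waiver patients, and up to 14 days' delay, usually only when the last patient in a cohort fails the Day 1 criteria. Escalation would also be slightly less frequent, by the amounts illustrated above.
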